## **2.2. Endpoints**

### **2.2.1. Primary Endpoint – Efficacy**

#### **Primary Endpoint for Patients with Late-stage HAT**

A patient will be considered as a success, in accordance with the WHO criteria (23), if the patient is alive with no evidence of trypanosomes in any body fluid and a CSF WBC equal to or below 20/ $\mu$ l 18 months after receiving acoziborole.

A patient with no parasitological evidence of a relapse and a CSF WBC above 20/ $\mu$ L or who, in the Investigator's opinion, requires rescue treatment will be considered as a probable relapse.

A patient who refuses the end-of-study lumbar puncture will be classified as a probable cure (success) in the absence of any clinical signs or symptoms suggestive of THA or with another obvious aetiology, provided that the outcome was favourable, i.e. a CSF WBC equal to or below 20/ $\mu$ l, at the last available assessment at 6 months or later.

Death for any reason, patients lost to follow-up and not retrieved or patients who refuse a lumbar puncture at 18 months and who had an unfavourable outcome earlier (probable relapse) will be considered as failures, with the exception of patients who fled the region due to armed conflict or natural disaster. These patients will be replaced by patients from another centre in order to maintain the planned sample size. In order to allow for replacement of some patients lost to follow-up due to armed conflict and to maintain the planned sample size of 155 evaluable patients, 7 additional patients will be enrolled in the study.

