## 9.8. Handling of Missing Data and Patients Lost to Follow-up

The primary endpoint is the outcome at 18 months. If outcome assessed at the final visit is missing, the **primary imputation method** will consist in imputing a probable success (considered as a success) to patients who attended the 18-month visit, but who refused the lumbar puncture planned at the visit, who showed no signs or symptoms of HAT at 18 months, who did not subsequently report any symptoms of relapse and for whom the outcome was considered as favourable at the last available assessment (17). If these criteria are not fulfilled, the patients will be considered as treatment failures. The outcome for patients who did not attend the 18-month visit or later will also be considered as a failure, except for patients who fled the region due to armed conflict or natural disaster.

Because the historical data may not allow for other imputation methods to be applied, only the primary imputation method will be used. The method will be described in detail in the SAP. Sensitivity analyses will be performed to assess the impact of missing data on acoziborole. The method will be described in detail in the SAP.

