## 10. KEY DERIVED VARIABLES

### 10.1. Outcome at 18 months

| Derivation algorithm for stage 1 and intermediate stage (month 18)   | Derivation algorithm for stage 2 (Month 18)  |
|--|--|
| 
Patient is → 1: Dead (any reason of death and any time between drug intake and M18) ⇒ Failure (stop)
         ↓
         Alive
         ↓
 Patient requires rescue medication for HAT at M18 or required it before (between drug intake and M18)
         → YES → 2: (definitive) Failure (stop)
         ↓
         NO rescue medication so far
         ↓
 Evidence of trypanosomes in any body fluid between drug intake and M18 visit ⇒ YES ⇒ 3: (definitive) Failure (stop)
         ↓
         NO observed trypanosomes
         ↓
 Patient Lost to follow-up at M18 (no survival information at M18 and later)
         → YES ⇒ 4: Failure (Stop) [a,b]
         ↓
         NO (the patient is not lost to follow-up)
         ↓
 Non-hemorrhagic lumbar puncture at M18 and WBC in CSF at M18 > 20 cells
         → YES ⇒ 5: Failure (stop)
         ↓
         NO (WBC in CSF at M18 ≤ 20 cells or no reliable data concerning WBC in CSF at M18)
         ↓
 Non-hemorrhagic lumbar puncture at M18 and WBC in CSF ≤ 20 cells
         → YES ⇒ 6: Success (stop)
         ↓
         NO (hemorrhagic CSF sample or no lumbar puncture at M18 for any reason)
         ↓
 No lumbar puncture at M18 or no reliable count of WBC in CSF at M18 but reliable number of WBC in CSF reported later (M24 or other additional visit)
         → YES ⇒ WBC in CSF > 20 ⇒ 7: Failure (Stop)
         → YES ⇒ WBC in CSF ≤ 20 ⇒ 8: Success (Stop)
         ↓
         NO (No lumbar puncture at M18 and no later reliable count of WBC in CSF)
 | 
Patient is → 1: Dead (any reason of death and any time between drug intake and M18) ⇒ Failure (stop)
         ↓
         Alive
         ↓
 Patient requires rescue medication for HAT at M18 or required it before (between drug intake and M18)
         → YES ⇒ 2: (definitive) Failure (stop)
         ↓
         NO rescue medication so far
         ↓
 Evidence of trypanosomes in any body fluid between drug intake and M18 visit ⇒ YES ⇒ 3: (definitive) Failure (stop)
         ↓
         NO observed trypanosomes
         ↓
 Patient Lost to follow-up at M18 (no survival information at M18 and later)
         → YES ⇒ 4: Failure (Stop) [a,b]
         ↓
         NO (The patient is not lost to follow-up)
         ↓
 Non-hemorrhagic lumbar puncture at M18 and WBC in CSF at M18 > 20 cells
         → YES ⇒ 5: Failure (stop)
         ↓
         NO (WBC in CSF at M18 ≤ 20 cells or no reliable data concerning WBC in CSF at M18)
         ↓
 Non-hemorrhagic lumbar puncture at M18 and WBC in CSF ≤ 20 cells
         → YES ⇒ 6: Success (stop)
         ↓
         NO (hemorrhagic CSF sample or no lumbar puncture at M18 for any reason)
         ↓
 No lumbar puncture at M18 or no reliable count of WBC in CSF at M18 but reliable number of WBC in CSF reported later (M24 or other additional visit)
         → YES ⇒ WBC in CSF > 20 ⇒ 7: Failure (Stop)
         → YES ⇒ WBC in CSF ≤ 20 ⇒ 8: Success (Stop)
         ↓
         NO (No lumbar puncture at M18 and no later reliable count of WBC in CSF)
 |

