
| Derivation algorithm for stage 1 and intermediate stage (month 18)   | Derivation algorithm for stage 2 (Month 18)  |
|--|--|
| 
Earlier (before M18) unfavorable outcome: increase of WBC in CSF at M6 or M12 with respect to EOH
 
⇒ YES ⇒ 9: Failure (stop)
 
↓
 
NO (no information or no earlier unfavorable assessment)
 
↓
 
Patient has clinical signs or symptoms at M18 evoking a failure
 
⇒ YES ⇒ 10: Failure (stop)
 
↓
 
NO (no clinical signs or symptoms evoking a relapse at M18)
 
↓
 
WBC in CSF ≤ 20 at M12 or absence of LP at M12 and for both cases no increase WBC in CSF at M6 with respect to EOH and no sign and symptoms at M18 evoking a relapse:
 
⇒ YES ⇒ 11: Success (stop) [b]
 
↓
 
NO (at least one criterion not met)
 
↓
 
Patient refused all post treatment lumbar punctures
 
⇒ YES ⇒ 12: Failure (stop) [a,b]
 
↓
 
All other cases ⇒ 13. Failure
 | 
Earlier (before M18) unfavorable outcome: WBC in CSF > 50 at M6 or WBC in CSF > 20 at M12 or increasing between M6 and M12
 
⇒ YES ⇒ 9: Failure (stop)
 
↓
 
NO (no information or no earlier unfavorable assessment)
 
↓
 
Patient has clinical signs or symptoms at M18 evoking a failure
 
⇒ YES ⇒ 10: Failure (stop)
 
↓
 
NO (no clinical signs or symptoms evoking a relapse at M18)
 
↓
 
WBC in CSF ≤ 20 at M12 or in absence of LP at M12 and for both cases WBC in CSF ≤ 50 at M6 and no signs and symptoms at M18 evoking a relapse:
 
⇒ YES ⇒ 11: Success (Stop) [b]
 
↓
 
NO (at least one criterion not met)
 
↓
 
Patient refused all post treatment lumbar punctures
 
⇒ YES ⇒ 12: Failure (Stop) [a,b]
 
↓
 
All other cases ⇒ 13. Failure
 |

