| 
No lumbar puncture at M12 or no reliable count of WBC in CSF at M12 but reliable number of WBC in CSF reported later (M18 or other additional visit)
 
⇒ YES ⇒ WBC in CSF > 20 ⇒ 7: Failure (Stop)
 
⇒ YES ⇒ WBC in CSF ≤ 20 and no signs or symptoms evoking a relapse ⇒ 8: Success (Stop)
 
↓
 
NO (no later reliable count of WBC in CSF)
 
↓
 
No reliable WBC count in CSF at M12 and later and Failure at M18 for any reason
 
⇒ YES ⇒ 9: Failure at M12 (Stop)
 
↓
 
NO
 
↓
 
No reliable count of WBC in CSF at M18 and M12 but WBC counts at M6 available and no signs and symptoms evoking a failure at M12 or M18
 
⇒ YES ⇒ WBC in CSF at M6 ≤ 5 and smaller than WBC in CSF at EOH ⇒ 10: Success (stop) [b]
 
⇒ NO ⇒ WBC in CSF at M6 > 5 or larger than WBC in CSF at EOH ⇒ 11: Failure (stop)
 
↓
 
NO (no lumbar puncture at M6, M12 and M18)
 
↓
 
Patient refused all post-treatment lumbar punctures but was met at M24 or later with no signs and symptoms evoking a relapse (normal activity)
 
⇒ YES ⇒ 12: Success at M12 [b]
 
↓
 
NO (Patient not met at M24 or later)
 
↓
 
Patient refused all post treatment lumbar punctures ⇒ YES ⇒ 13: Failure (Stop) [a,b]
 | 
No lumbar puncture at M12 or no reliable count of WBC in CSF at M12 but reliable number of WBC in CSF reported later (M18 or other additional visit)
 
⇒ YES ⇒ WBC in CSF > 20 ⇒ 8: Failure (Stop)
 
⇒ YES ⇒ WBC in CSF ≤ 20 ⇒ 9: Success (Stop)
 
↓
 
NO (no later reliable count of WBC in CSF)
 
↓
 
No reliable WBC count in CSF at M12 and later and Failure at M18 for any reason
 
⇒ YES ⇒ 10: Failure at M12 (Stop)
 
↓
 
NO
 
↓
 
No reliable count of WBC in CSF at M18 and M12 but WBC counts at M6 available and no sign and symptoms evoking relapse at M12 or M18
 
YES ⇒ WBC in CSF at M6 ≤ 20 cells ⇒ 11: Success (stop) [b]
 
NO ⇒ WBC in CSF at M6 > 20 cells ⇒ 12: Failure
 
↓
 
NO (no lumbar puncture at M6, M12 and M18)
 
↓
 
Patient refused all post-treatment lumbar punctures but was met at M24 or later with no signs and symptoms evoking a relapse (normal activity)
 
⇒ YES ⇒ 13: Success at M12 [b]
 
↓
 
NO (Patient not met at M24 or later)
 
↓
 
Patient refused all post treatment lumbar punctures ⇒ YES ⇒ 14: Failure (Stop) [a,b]
 |

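### For stage 2 patients without a CSF count at M18 or later, SAP 10.1 tests for relapse signs only at M18 and omits Protocol 9.8's condition that no relapse symptoms are reported afterwards

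*SAP*

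**What the plan says.** Protocol 9.8 sets the primary imputation rule for a missing 18-month outcome. A patient who came to the visit but refused the puncture is imputed a success if the patient is one "who showed no signs or symptoms of HAT at 18 months, who did not subsequently report any symptoms of relapse", and if the last available assessment was favourable. The default is explicit: "If these criteria are not fulfilled, the patients will be considered as treatment failures".

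SAP 7.6.1 hands missing-data handling for the primary analysis entirely to the Section 10 algorithm. In the stage 2 column of SAP 10.1, a patient with no reliable CSF count at M18 or later reaches boxes 9 to 13. Box 10 gives failure if "Patient has clinical signs or symptoms at M18 evoking a failure". Box 11 gives success if the M12 count is at most 20 or there was no M12 puncture, the M6 count is at most 50, and there are "no signs and symptoms at M18 evoking a relapse". The SAP 6.1 failure definition also limits signs and symptoms to M18.

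The protocol is not uniform. For a patient who refuses the final puncture, Protocol 2.2.1 requires only that the outcome was favourable earlier and that the patient is judged "in the absence of any clinical signs or symptoms suggestive of THA or with another obvious aetiology". Neither 2.2.1 nor the 18-month row of Protocol Table 1 mentions symptoms reported later.

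**The concern.** A patient in box 11 is an imputed cure: there is no CSF count at the endpoint. Protocol 9.8 attaches a safeguard to that imputation, namely that later reports of relapse cancel it. The SAP drops the safeguard from the primary endpoint without saying so. Section 11 lists changes to adverse-event counting, stage wording and the yardstick studies, but not this one.

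The omission can act in one direction only, towards a higher success rate. The study has no formal success rule, so the rate and its lower confidence bound are what will be read against the historical NECT results.

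**Working it through.** **1. Trace of one stage 2 patient.** Assumed data: M6 count 10, M12 count 5, puncture refused at M18, no CSF count then or later, well at M18, relapse symptoms reported at a later contact.

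| SAP 10.1, stage 2 | Test | Result |
|---|---|---|
| Boxes 1–4 | Death, rescue or trypanosomes up to M18; lost to follow-up | None applies |
| Boxes 5–6 | Reliable count at M18 | None available |
| Boxes 7–8 | Reliable count later | None available |
| Box 9 | M6 > 50, or M12 > 20, or rise from M6 to M12 | No (10, then 5) |
| Box 10 | Signs at M18 | No |
| Box 11 | M12 ≤ 20, M6 ≤ 50, no signs at M18 | **Success** |

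Under Protocol 9.8 the same patient breaks the condition on later symptoms and is a **failure**.

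Two variants mark the limits. With a later count of 60, box 7 returns failure. With an M12 count of 25, box 9 returns failure. The gap therefore needs favourable earlier counts and no later count.

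**2. Does other text close the gap?**
- The data review committee in SAP 6.1 checks status with this same algorithm.
- The SAP 7.5 time-windows are stated not to apply to the primary endpoint.
- Box 3 does not reach further: it looks for "Evidence of trypanosomes in any body fluid between drug intake and M18 visit". Box 2, on rescue, also stops at M18.

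**3. Are later data expected?** Yes. Boxes 7 and 8 use CSF counts from month 24 or another extra visit. Protocol 6.4.4 provides return visits for suspected relapse, and Protocol 9.3 counts attendance beyond the 18-month window.

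**4. Size.** Jeffreys interval: the 2.5% and 97.5% quantiles of Beta(x + 0.5, n − x + 0.5), with n = 155 from Protocol 9.1.

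The plan's own figures reproduce:
- 138/155 = 89.0%: 83.40–93.23, width 9.83 (stated 83.4–93.2, width 9.8).
- 146/155 = 94.2%: 89.67–97.09, width 7.42 (stated 89.7–97.1, width 7.4).

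Each patient moved from success to failure costs 1/155 = 0.65 points. The number k of such patients is not in the documents, so the range below is an assumption.

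| Start | k = 1 | k = 3 | k = 5 |
|---|---|---|---|
| 146/155, 94.2% (89.7–97.1) | 93.5% (88.9–96.6) | 92.3% (87.3–95.7) | 91.0% (85.7–94.7) |
| 138/155, 89.0% (83.4–93.2) | 88.4% (82.6–92.7) | 87.1% (81.2–91.7) | 85.8% (79.7–90.6) |

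**The case against.** **Few patients can be affected.** No visit is scheduled after M18, and the 46-month total is simply 28 months of enrolment plus 18 of follow-up. Protocol 6.4.4 provides CSF sampling at an unscheduled visit when symptoms suggest relapse, so a symptomatic patient would often have a count, and a count above 20 already fails at box 7. What remains is mainly a second refusal or an unreliable sample after favourable earlier results. This stands, and it limits the size, not the contradiction.

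**The protocol disagrees with itself.** SAP 6.1 fits Protocol 2.2.1 and Table 1, which are silent on later symptoms. This also stands. But 9.8 is the section that defines the primary imputation, and silence elsewhere does not cancel its condition.

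**Sensitivity analyses cover these patients.** The fair-case method resamples box 11 outcomes and the observed-case method sets missing M18 data to missing. Both show how far the rate depends on imputed cures, but neither uses later symptoms and neither changes the primary estimate.

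A reader might also infer more than the documents support:

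- *That later contact can earn a success but never a failure.* SAP 10.2 has a rule for a case where "Patient refused all post-treatment lumbar punctures but was met at M24 or later with no signs and symptoms evoking a relapse". It belongs to the secondary 12-month outcome. A stage 2 patient with no puncture has no M6 count, cannot meet box 11 of 10.1 and fails at box 12; box 10 of 10.2 then returns failure before the month-24 rule in box 13 is reached.
- *That the stage 1 and intermediate column contradicts the protocol in the same way.* Protocol 9.8 addresses the late-stage primary endpoint. Protocol 2.2.2 has its own 18-month rule for the other cohort, without a later-symptom condition.
- *That Protocol 9.8 makes rescue or trypanosomes after M18 a failure.* It names symptoms only. Adding trypanosomes for patients without a count would sit oddly beside box 8, where a later count of 20 or less gives success.

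**Conclusion.** The stage 2 algorithm is wrong as written against Protocol 9.8, and the departure is undeclared. It classes as a success a patient whom the protocol classes as a failure: one who refuses the M18 puncture, meets the other box 11 conditions, and later reports relapse symptoms without a CSF count.

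The contradiction is strict for refusers who attended M18, the group that 9.8 describes. Boxes 9 to 13 also take in haemorrhagic samples and punctures missed for other reasons.

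Any bias is upwards, by 0.65 points per patient if 155 are analysed. The count is unknown and probably small. It would be tempting to say that a patient or two could carry the rate across the 94.1% pooled NECT figure. That is arithmetically possible, but nothing in the plan turns on crossing it, and the number of such patients would have to be assumed.

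**What to change.** - **SAP 10.1, stage 2 column:** reword the symptom test in boxes 10 and 11 to cover signs or symptoms at M18 or relapse symptoms reported afterwards. Make the same change in the SAP 6.1 failure definition.
- **Protocol:** reconcile 2.2.1 and the 18-month row of Table 1 with 9.8.
- **Stage 1 and intermediate column:** the sponsor should decide, and state, whether the same condition applies, given the separate rule in Protocol 2.2.2.
- **Rescue treatment recorded after M18:** reconcile SAP 6.3, which counts a decision to use it at any time after dosing, with box 2 of 10.1, which stops at M18.

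If the sponsor prefers to keep the M18 limit, SAP Section 11 should list it as a departure from Protocol 9.8, with the reason.

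The cost is a few edited phrases and the matching program lines, using later contacts that the SAP already expects. The success rate can only stay the same or fall slightly. One drawback should be acknowledged: time under observation after M18 may differ between patients, since those enrolled first could be seen for up to about 28 months longer than those enrolled last.

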##### **Endpoints in Patients with Early- or Intermediate-stage HAT**

Two efficacy endpoints will be used for patients with early- and intermediate-stage HAT: the outcome at 12 months and the outcome at 18 months after receiving treatment. A patient will be considered as a success at 12 months if the patient is alive with no evidence of trypanosomes in any body fluid and if the CSF

WBC is equal to or less than 20/ $\mu$ L. A patient with no parasitological evidence of relapse, but with a CSF WBC above 20/ $\mu$ L or who, in the Investigator's opinion, requires rescue treatment, will be considered as a relapse. A patient who refuses the lumbar puncture at 12 months will be classified as a probable cure (success) in the absence of any clinical signs or symptoms suggestive of THA or with another obvious aetiology, provided that the outcome was favourable, i.e. a CSF WBC equal to or less than 5/ $\mu$ L, at 6 months. Death for any reason, patients lost to follow-up and not retrieved or patients with no post-treatment lumbar puncture will be considered as failures, with the exception of patients who fled the region due to armed conflict or natural disaster. For memory, patients who fled the region due to armed conflict or natural disaster will not be included in the mITT population and will therefore not be taken into account in the calculation of the success rate. A patient with early- or intermediate-stage HAT will be considered as a **success** at 18 months if the CSF WBC is equal to or below 20/ $\mu$ L and in the absence of trypanosomes, rescue treatment and signs or symptoms suggestive of a relapse. If the patient does not have a lumbar puncture at 18 months, the outcome at 6 months or at 12 months will be used.

A patient with early- or intermediate-stage HAT will be considered as a success at 6 months and at 12 months if the CSF WBC is equal to or less than 20/ $\mu$ L and in the absence of trypanosomes, rescue treatment and signs or symptoms suggestive of a relapse. If the patient does not have a lumbar puncture at 6 months, the outcome at 12 months and, if necessary, at 18 months will be used. If the patient does not have a lumbar puncture at 12 months, the outcome at 18 months will be used and, if necessary, the outcome at 6 months will be used. If no post-treatment lumbar punctures were performed, the outcome will be considered as unfavourable.

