#### Endpoint at 18 months in Patients with Stage 1 and Intermediate-stage HAT

The response (success or failure) at 18 months in patients with stage 1 and intermediate stage HAT will be derived from the algorithm presented in [Section 10.1](#).

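### For stage 1 and intermediate-stage patients, box 11 of the SAP's 18-month algorithm does not handle a missing 6-month CSF count, and either way of reading it conflicts with the protocol

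*SAP*

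**What the plan says.** SAP 6.2 states: "The response (success or failure) at 18 months in patients with stage 1 and intermediate stage HAT will be derived from the algorithm presented in", and the place it points to is 10.1. That section is a chain of numbered exits, called boxes here, with one column for stage 1 and intermediate stage (cohort 2) and one for stage 2.

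Take a cohort 2 patient who is alive, has had no rescue treatment, shows no trypanosomes, is not lost to follow-up and has no reliable CSF count at M18 or later. Boxes 9 to 13 decide:

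- **Box 9:** Failure on "increase of WBC in CSF at M6 or M12 with respect to EOH". The other exit reads "NO (no information or no earlier unfavorable assessment".
- **Box 10:** Failure if there are signs of relapse at M18.
- **Box 11:** Success, flag [b], if the M12 count is at most 20/µL or there is "absence of LP at M12 and for both cases no increase WBC in CSF at M6 with respect to EOH", with no signs at M18. The other exit reads "NO (at least one criterion not met".
- **Box 12:** "Patient refused all post treatment lumbar punctures" leads to Failure, flags [a,b].
- **Box 13:** everything else is Failure.

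Flag [a] turns the patient into a success in the best-case analysis. Flag [b] marks the patient for resampling in the fair-case analysis.

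Protocol 2.2.2 says that, for cohort 2, a missing 18-month puncture is replaced by the 6- or 12-month outcome. Its 12-month definition says "patients with no post-treatment lumbar puncture will be considered as failures" (displacement by conflict or disaster aside). Its paragraph on the 6- and 12-month outcomes likewise makes the result unfavourable when no puncture followed treatment. SAP 11 declares no departure from these rules.

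**The concern.** Box 11 tests for the absence of an increase and never asks that a count exist. The stage 2 column asks for an M6 count of at most 50/µL, so a missing count cannot satisfy it. In cohort 2 the class of a patient without an M6 count depends on how a programmer treats a comparison with a missing value, and the SAP gives no instruction.

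The class feeds several results: the cohort 2 18-month success rate, the overall 18-month rate, the Fisher comparison of the cohorts, the trend tests across stages and subgroups, the cohort 2 by-centre results and the cohort 2 model over visits. If missing is taken as no increase, stage 2 and cohort 2 also class the same record differently.

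**Working it through.** **Inputs.** Boxes 9 to 13 of SAP 10.1, cohort 2 column; SAP 7.6.1, 10.2 and 10.3; Protocol 2.2.2; about 50 cohort 2 patients and an expected success rate around 91%, both from Protocol 9.1.

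**Step 1. Trace three patients.** Each is alive, free of signs at M18 and without a count at M18 or later. The D11 puncture supplies the EOH count.

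| Patient | Missing M6 taken as no increase | Observed M6 count required | Protocol 2.2.2 |
|---|---|---|---|
| No puncture at all after treatment (all declined) | Box 11, Success | Box 12, Failure | 6- or 12-month outcome, which is unfavourable |
| D11 count 4, nothing later (M6, M12, M18 all declined) | Box 11, Success | Box 12 or 13, Failure (depends on whether D11 counts as a post-treatment puncture) | No favourable M6 or M12 outcome to carry forward |
| D11 count 4, M12 count 3, no M6 puncture | Box 11, Success | Box 13, Failure | 12-month outcome, which is favourable |

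The first reading is wrong for the first patient and lacks support for the second. The second reading is wrong for the third patient. In the stage 2 column the first patient reaches box 12, Failure.

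**Step 2. Can box 12 be reached?** Let the EOH, M6 and M12 counts each be missing or one of 0, 3, 10, 18, 25 or 60, with M18 signs present or absent. That gives 7 × 7 × 7 × 2 = 686 records. If missing means no increase, box 12 is reached in 0 of 686. If an M6 count is required, it is reached in 7 of 686 when the D11 puncture is not counted as post-treatment, and in 1 of 686 when it is.

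**Step 3. Compare with the rest of the SAP, first reading.** Take a patient who declined every puncture.

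- M6: Failure (10.3, box 6, no reliable count).
- M12: the patient follows the branch "NO (no lumbar puncture at M6, M12 and M18" in 10.2 and, unless met at M24 or later, is Failure at box 13.
- M18: Success, with no new CSF information.
- The best-case method in 7.6.1 is meant to convert such patients from failure to success. On this reading the main and best-case results coincide for them.

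**Step 4. Size.** One patient is 1/50 = 2.0 points. Jeffreys limits are the 2.5% and 97.5% points of Beta(x + 0.5, n − x + 0.5). As a check, n = 155 at 89% returns 83.4–93.2, as in Protocol 9.1. For n = 50 and 45 successes the width is 96.1 − 79.5 = 16.6 points, against about 17 in the plan.

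The documents do not say how many patients are affected. Assuming 0 to 3, and an illustrative 46 successes on the first reading:

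| Reclassified to Failure | Rate | 95% Jeffreys interval |
|---|---|---|
| 0 | 46/50 = 92% | 82.1–97.2 |
| 1 | 45/50 = 90% | 79.5–96.1 |
| 2 | 44/50 = 88% | 76.9–94.8 |
| 3 | 43/50 = 86% | 74.5–93.5 |

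On the second reading the shift is also 2 points per patient, in the other direction.

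**The case against.** A reader might infer that the SAP counts patients without CSF evidence as cured, that box 12 is dead, and that the result is biased in favour of acoziborole. The documents do not establish this. All three follow only if a missing M6 count meets the no-increase test, and the SAP never says that it does. Box 9's exit names missing information separately from the absence of an unfavourable finding. Box 9 has also removed every observed M6 increase, so the M6 clause in box 11 adds something only if it demands a count. Box 12, its [a] flag and the best-case method all presuppose that refusers fail. This evidence is not decisive, because box 11 also repeats the M18 signs already tested in box 10, so redundancy there proves little.

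Other points against:

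- Having no puncture at M6, M12 and M18 is wider than having refused every puncture. A puncture can be missing for another reason, and D11 is itself after treatment. This stands, and the fix respects it.
- The documents are not uniformly strict. Protocol Table 1 lists a sign-free patient who refuses the 18-month puncture as favourable. SAP 10.2 box 12 gives M12 success to a refuser met well at M24 or later. But Table 1 is the clinical classification in the rescue-treatment section; the cohort 2 endpoint is defined in Protocol 2.2.2.
- Requiring an M6 count would only align cohort 2 with stage 2. That is true, but for cohort 2 it breaks the protocol's fallback to the 12-month outcome.
- The endpoint is secondary and descriptive, with no success rule. The Evaluable set removes refusers who are not failures, and the fair-case method resamples both box 11 and box 12. These limit the damage without settling the main derivation.

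**Conclusion.** The point holds as a defect in the rule: no reading of box 11 implements Protocol 2.2.2. One reading gives Success where the protocol's fallback is unfavourable. The other gives Failure where the fallback is favourable. The direction of any error therefore depends on a choice the SAP does not make.

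The effect is 2 points per affected patient at n = 50. One reclassification in the illustration moves the rate from just above the expected 91% to just below it. The count of 0 to 3 patients and the 46 successes are assumptions, and the true number may be zero. A patient is affected only if followed to M18, free of signs, without a usable count from M18 on, and without an M6 count. The scope is the cohort 2 and overall 18-month rates and the analyses that use them. The stage 2 primary analysis uses the other column and is untouched.

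**What to change.** In the cohort 2 column of SAP 10.1:

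1. Place box 12 before box 11, with its wording and [a,b] flags unchanged. Best-case success then stays limited to the patients named in SAP 7.6.1.
2. Make box 11 require at least one reliable M6 or M12 CSF count, the latest available being at most 20/µL, no increase over EOH (already tested in box 9) and no signs at M18.
3. Send patients with no such count who did not refuse every puncture to box 13, Failure, without flag [a].

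A missing M6 count alone then neither helps nor harms. In the table above, the first patient becomes Failure, the second Failure (the D11 question affects only the flags) and the third Success.

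Check boxes 9 to 13 of the cohort 2 column in SAP 10.2 against the new M18 status. Box 9 there fails anyone without an M12 or later count who is an M18 failure, so it would pre-empt boxes 12 and 13. An M6-only count of 6 to 20/µL, not above EOH, would be Success at M18 but Failure at M12, as it already is under the present text.

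The cost is a small wording and program change and a possibly slightly less favourable cohort 2 rate. A patient with EOH 25, M6 22 and no M12 puncture would move from Success to Failure, in line with the protocol's limit of 20/µL at 6 months.
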